Chewing gum stimulates salivation, neutralizes, and raises pH levels, serving as a medium for administering therapeutic agents. However, global increases in sugar consumption have led to the development of chewing gums containing sugar substitutes such as polyols or non-fermentable sugars, with the most common being nutritive sweeteners like sorbitol and xylitol. The use of polyolcontaining chewing gum could play a role in preventing dental caries compared to not using gum or using sugared gum, most likely due to increased salivary flow and pH, thereby improving enamel lesion remineralization. However, xylitol has anticariogenic properties influencing the reduction of dental plaque. Objective: To evaluate the effects of xylitol-based chewing gum, both sugar-free and sugared, on salivary flow and pH in young adults. Methodology: This is a quantitative, analytical, experimental study through a double-blind parallel randomized controlled trial. The population will consist of all students enrolled (1275 students in the period October 2022-February 2023) in the Dentistry program at the Catholic University, aged 18 to 25, who voluntarily meet the inclusion criteria. The sample size will be 21 participants in each group, adjusted for a 15% loss of information or study dropout, thus requiring 25 participants in each group. Participants meeting the selection criteria will be assigned probabilistically using simple random sampling through a lottery system to four groups: the first group (G1) will consume gum with 100% xylitol, the second group (G2) will consume sugar-free gum with sorbitol, maltitol, mannitol, and xylitol, the third group (G3) will consume sugared gum containing sugar, dextrose, glucose, sweeteners such as aspartame and acesulfame-K, and the fourth group (G4, control) will chew paraffin. Data will be entered into an Excel matrix and analyzed using SPSS v.25. Descriptive analysis of the data will be conducted. Chi-square will be used for demographic data, Levene's test will determine data homogeneity, and ANOVA will determine mean differences, followed by Tukey's post-hoc comparison to find significant differences between group means, with a significance level of p <0.05. Expected Results: It is expected that salivary pH and flow means will differ among the different chewing gums.

RESEARCH PROBLEM

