Xylitol is considered cariostatic due to its ability to decrease counts of Streptococcus mutans (SM)^{12,14} and Lactobacillus (LB)⁴, as well as its role in controlling dental plaque formation and, consequently, the incidence of dental caries. Therefore, it is particularly effective in conditions where proper oral hygiene is not possible¹², or as a complement to toothbrushing for oral hygiene.^{14,15} Additionally, it stimulates salivary secretion, an important factor in maintaining alkaline pH, and promotes mechanical cleansing of tooth surfaces.¹³

Its mechanism of action is to create an unfavorable environment for bacterial growth, especially for Streptococcus mutans (SM), as it reduces its ability to adhere to oral tissues by affecting the insoluble glucans involved in this process. This property reduces the possibility of dental plaque formation and, therefore, the local effect of lactic acid. Additionally, xylitol penetrates the bacterial

cytoplasm, interfering with glycolysis and inhibiting the growth of microorganisms.¹²

Furthermore, its action affects other species such as Streptococcus sobrinus (SS) and Actinomyces viscosus (AV). As a result, a less cariogenic environment is created. ¹² Tapiainen et al. ¹⁶ stated that the effect of xylitol disappears from saliva within 15 minutes.

Sorbitol is a hexitol derived from glucose with low cariogenic potential. Like xylitol, it causes a decrease in SM, SS, AV, LB, and insoluble glucans, along with an increase in salivary pH, giving it anticariogenic potential. Current evidence establishes that pentitols like xylitol, as well as hexitols like sorbitol, have good results in reducing dental caries. However, pentitols are more effective and therefore more commonly used. ^{4,12}

RESEARCH OBJECTIVES

General Objective

Compare the effects of xylitol-based chewing gum (Xylichew), sugar-free (Trident), and sugared (Agogó) on salivary flow rate and pH in young adults

Specific Objectives

Determine the initial salivary flow, at 10, 20, and 30 minutes after the consumption of xylitol-based, sugar-free, and sugared chewing gums in young adults.

Determine the initial salivary pH, at 10, 20, and 30 minutes after the consumption of xylitol-based, sugar-free, and sugared chewing gums in young adults.

RESEARCH QUESTION OR STUDY HYPOTHESIS

H0: The consumption of different chewing gums does not produce changes in the level and flow of initial salivary pH at 10, 20, and 30 minutes.

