H1: The consumption of different chewing gums results in changes in the level and flow of initial salivary pH at 10, 20, and 30 minutes.

METHODOLOGY

Research Design

- It is a quantitative, analytical, experimental study conducted through a double-blind, parallel randomized controlled trial.
 - Definition of the study population and, if applicable, it is necessary to detail how the sample size calculation was performed (formulas and development).

The population will consist of all enrolled students (1275 students in the period September 2023-February 2024) in the Dentistry program at the Catholic University, aged between 18 and 25 years old, who voluntarily meet the inclusion criteria.

For the sample size calculation, an online calculator was used, employing the formula for comparing two means. A confidence level of 95% and a statistical power of 90% were set. Based on a previous study that reported a desired difference of 1 unit, with a precision and variance of 1 in the reference or control group, it was determined that 21 participants would be needed in each group. However, to account for potential information loss or dropout from the study, the sample size was adjusted by 15%, resulting in the requirement of 25 participants in each group. (Figure 1)

$$n = \frac{2\left(Z_{\alpha} + Z_{\beta}\right)^2 * S^2}{d^2}$$

Figure 1. Hypothesis testing formula for determining means.¹⁴

Replacing the formula

n= participants needed in each of the groups

 $Z\alpha = Z$ value corresponding to the desired risk 0.05 = 1.96

 $Z\beta = Z$ value corresponding to the desired risk 90%= 1.282

 S^2 = Variance of the quantitative variable in the control group =1

d= Minimum detectable difference desired = 1

$$n = \frac{2(1.96 + 1.282)^2 * 1^2}{1^2} = 20.99$$

• List of establishments where observational or intervention research will be conducted on human subjects. It is necessary to specify whether the institutions are public or private and include their postal address and letter of interest (Appendix B)

The intervention will take place among students of the Dentistry program at the University of Cuenca, main campus, in the Molecular Biology laboratory. Sampling and determination of salivary flow and pH level will be carried out there. (Appendix B)

• Inclusion Criteria

Within the selection criteria, the inclusion criteria will be participants with at least 20 teeth, providing written informed consent, and being willing to comply with the study procedures.

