• Exclusion Criteria

The exclusion criteria will be individuals with systemic, infectious, or inflammatory diseases or those taking medications, antibiotics, or fluoride in the last month; regular consumers of products and mouthwashes containing xylitol or sorbitol, with abnormal salivary flow (<1 ml/min), pregnant women or those on contraceptive pill treatment, or with eating disorders (anorexia and bulimia); subjects with periodontal disease or presence of dental caries.

• The variables described in this section should be consistent with those mentioned in (APPENDIX C) the table of operationalization of the variables

The variables of interest will be chewing gums, salivary flow level, and salivary pH during 4 time periods: initial (without chewing gums), at 10, 20, and 30 minutes after consuming the chewing gums.

Detailed and sequential description of all procedures that will be carried out to achieve each of the stated objectives. At least the following should be included.

7.1 Procedures: Students will be invited to participate through the study's presentation in each and every classroom of the students enrolled in the period September 2023-February 2024. At the end of the presentation, they will be invited to sign the informed consent, a document in which participants will provide their cell phone numbers so that they can be contacted via WhatsApp messages for the preliminary examination of their oral cavity to verify compliance with the inclusion criteria, as well as for sample

collection.

7.2 Sample Selection: Participants who meet the selection criteria will be probabilistically assigned using simple random sampling through a lottery system and will be assigned to each group. There will be 4 groups: the first group, G1, will consume chewing gums with 100% xylitol; the second group, G2, will consist of individuals who consume sugar-free chewing gums; the third group, G3, will consist of participants who chew sugared gums; and the fourth group, G4, will serve as the control group and will chew paraffin (Figure 2). This procedure will be carried out by investigator 1 (**Appendix D - Chewing Gum Information**)

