7.7 Information Management: Technician 1 will handle the physical documents until the laboratory process is completed. Subsequently, Technician 1 will provide the data matrix in Excel for further analysis by Investigator 1. Participants will not receive individual research results; instead, the final research results will be disseminated.

8. Human biological samples do not require exportation as they will be disposed of immediately after the determination of salivary flow and pH level.

9. Data Analysis Plan

The data analysis will be conducted using SPSS v.25. Descriptive analysis of the data will be performed. Chi-square test will be used for demographic data, Levene's test will determine the homogeneity of the data, and ANOVA test will be used to determine differences in means. Post-hoc Tukey's test will be employed to find significant differences between the means of the groups, with a significance level set at p<0.05. All analyses will be conducted by Investigator 1.

HUMAN AND MATERIAL RESOURCES

1. Enumerate the human resources that will participate in the research, detailing the functions each one will fulfill; it should coincide with the section.

1. Principal Investigator		Collecting the sample and measuring salivary flow and pH		
2. Investigator 1	Inviting participation via email and conducting statistical analysis			
3. Investigator 2	Sending study participation information via email.			
4. Technician 1		Collecting quantitative data on the data sheets.		
5. Technician 2		Collecting the sample.		

2. Provide a detailed description of all the material resources used for the execution of the project, including necessary information

Among the materials are nitrile gloves, masks, Falcon tubes, funnel, hand towels, xylitol chewing gums, Trident, Agogo, and paraffin. As for the equipment, a pH meter and a precision scale (Boeco) are needed.

ETHICAL AND GENDER CONSIDERATIONS

1. Provide a detailed description of the measures to be taken to ensure the rights of individuals to minimal risk, autonomy, and confidentiality

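### The protocol names no primary outcome, primary time or rule for supporting H1 across salivary flow and pH at 10, 20 and 30 minutes, and its sample size is tied to neither outcome.

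*Protocol*

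**What the plan says.** The General Objective is comparative: "Compare the effects of xylitol-based chewing gum (Xylichew), sugar-free (Trident", with sugared gum as the third product, on flow rate and pH. Two parallel Specific Objectives follow, one for flow and one for pH. The pH objective reads "Determine the initial salivary pH, at 10, 20, and 30 minutes after the consumption of xylitol-based, sugar-free, and sugared chewing gums", and the flow objective has the same form. The variables paragraph in Methodology lists both without ranking them: "The variables of interest will be chewing gums, salivary flow level, and salivary pH during 4 time periods".

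H1 (Research Question or Study Hypothesis) states that consuming different gums "results in changes in the level and flow of initial salivary pH at 10, 20, and 30 minutes". The summary's expected results say: "It is expected that salivary pH and flow means will differ among the different chewing gums".

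The sample-size paragraph is worded "Based on a previous study that reported a desired difference of 1 unit", with a variance of 1 in the control group. It reaches 21 per group, or 25 after 15% loss, and does not say whether the unit is pH or flow, or at which time.

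Section 9 provides for ANOVA and then Tukey's test "to find significant differences between the means of the groups, with a significance level set at p<0.05". It does not say how many ANOVAs will be run, whether they are per time or repeated-measures, or which of them decides H1. Nothing in the protocol text at hand names a primary outcome or a primary time. Appendix C, the table of variables, is not shown.

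**The concern.** There are two outcomes and three post-gum times, hence up to six between-group comparisons, each of which could be reported as the trial's answer at 0.05. Tukey's procedure protects the six pairs of the four groups inside one ANOVA. It gives no protection when the ANOVA is repeated for another outcome or another time.

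H1 does not settle the matter. Its joining of pH and flow can mean that both must change or that either may. Its reference to the initial value can be read as change from baseline within a gum, whereas Section 9 tests differences between groups. The same data could therefore be reported as supporting H1 or not, according to a rule chosen after the results are known.

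The choice of primary outcome is not a detail that can wait for a statistical analysis plan. It fixes the trial's question, and the sample size has to refer to it. Here the sample size refers to neither outcome.

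**Working it through.** **1. The protocol's own figure.** Inputs from the sample-size section: Zα = 1.96, Zβ = 1.282, S² = 1, d = 1.

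n = 2(1.96 + 1.282)² × 1 / 1² = 2 × 10.51 = 21.02. The protocol prints 20.99 and uses 21; the gap is immaterial here. With 15% loss, 21 / 0.85 = 24.7, so 25. The figure is reproduced, but it holds for any outcome with d equal to one SD. It is not specific to pH or flow.

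**2. The inputs against the spread the protocol quotes.** The Research Problem section reports, from an earlier gum study, SDs of 0.12–0.28 for pH and 0.31–0.45 for flow. All are well below the assumed SD of 1. Against those SDs a 1-unit difference would be:
- pH: 1 / 0.28 = 3.6 to 1 / 0.12 = 8.3 SD
- flow: 1 / 0.45 = 2.2 to 1 / 0.31 = 3.2 SD

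The pH gap between the two gums in that study was 7.98 − 7.49 = 0.49 at 2 minutes and 7.60 − 6.82 = 0.78 at 30 minutes, both below 1 unit. So d = 1 with S² = 1 matches neither outcome as quoted.

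**3. False support for H1 under different rules.** Assumptions: no true differences; 4 groups of 21; one one-way ANOVA per outcome and post-gum time, each at 0.05 (F critical 2.719, Tukey q critical 3.711); equal correlation between times. The protocol gives no correlations, so a range is shown. There were 40,000 simulated trials per setting, except the last row, which used 60,000.

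| Time correlation | Flow–pH correlation | Any of six ANOVAs | A gum-versus-gum Tukey difference after a significant ANOVA | Both outcomes significant at some time |
|---|---|---|---|---|
| 0 | 0 | 26.4% | 13.5% | 2.1% |
| 0.5 | 0 | 24.2% | 12.5% | 1.6% |
| 0.8 | 0 | 19.0% | 9.9% | 1.0% |
| 0.9 | 0 | 16.4% | 8.4% | 0.7% |
| 0 | 0.5 | 25.0% | 12.8% | 3.4% |
| 0.5 | 0.5 | 22.5% | 11.4% | 3.0% |
| 0.8 | 0.5 | 18.1% | 9.3% | 2.3% |
| 0.9 | 0.5 | 15.5% | 7.9% | 1.7% |
| 0.9 | 0.9 | 12.1% | 6.3% | not run |

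Analytic check for six independent tests: 1 − 0.95⁶ = 26.5%. With 25 per group instead of 21, the any-ANOVA range is 15.2–26.4%, so loss to follow-up does not change the picture.

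**4. Other structures that Section 9 allows.**
- One overall test per outcome (two tests): 9.1–10.0% for any significant test and 4.4–4.8% for a gum-versus-gum difference. Analytic check for two independent tests: 1 − 0.95² = 9.75%.
- One named outcome at one time: 4.8–5.1% and 2.3–2.4%.

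**The case against.** The strongest reply is that the large percentages come from assumptions the protocol does not make: that any one significant result suffices, that six separate ANOVAs are run, and that no group differs anywhere. This stands. Section 9 says only ANOVA, so a repeated-measures analysis or one test per outcome is possible, and H1 can be read as requiring both outcomes. A reader might infer that the trial has a false-positive rate of up to 27%. The documents do not support that: it is one end of one permitted reading, and the strictest reading tabulated falls below 5%. Nor is the range a bound. It drops to about 12% when both correlations are 0.9. The gum-versus-gum figure rises to 9–16% if paraffin truly differs and the three gums do not.

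It can also be said that pH is implicitly primary. The Research Problem section calls for trials of effectiveness on salivary pH, and Expected Results attaches significant differences to pH only. These are hints. The objectives, the hypotheses and the variables paragraph all treat the two outcomes alike.

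Two further inferences should be resisted. First, the sample size is not beyond checking: the quoted SDs allow the assumed SD of 1 to be examined, as above. Second, the background remark that "the effect of xylitol disappears from saliva within 15 minutes" might suggest that only the earliest time matters. It stands in an account of action on bacteria and mentions neither flow nor pH, and the quoted pH gap widens between 2 and 30 minutes. It gives no basis for preferring one time.

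**Conclusion.** The point holds as a gap in specification. The protocol has two equally ranked outcomes at three times, a 0.05 level with no control across them, no stated rule for H1, and a sample size tied to no outcome or time.

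The size depends on the rule eventually used. Under no true differences with 21 per group, false support for H1 is about 15–27% if any of six per-time ANOVAs counts (within-person correlation 0.9 to 0, flow–pH correlation 0 to 0.5). A false gum-versus-gum difference under the same conditions is about 8–13%. If both correlations are 0.9, the figures are about 12% and 6%. One overall test per outcome gives about 9–10%, and requiring both outcomes to differ gives about 1–3%. The correlations are assumptions throughout. What can be said without them is that the protocol does not fix which of these rates applies. This should be corrected before data are seen. Confidence is medium, because the form of the ANOVA and the decision rule are unstated.

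**What to change.** Before data are seen:
- In Section 9, name one outcome at one post-gum time as primary, tested at 0.05. The choice is the sponsor's.
- State that the conclusion on H1 rests on the between-group ANOVA for that outcome and time, followed by Tukey.
- Reword H0 and H1 so that they concern differences between groups in that outcome at that time.
- In the sample-size section, say that the 1-unit difference and the variance of 1 refer to that outcome and time, and justify them against the SDs quoted in the Research Problem section.
- Label the other outcome and the other times secondary.

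**Cost.** With the sample size kept as it is, this is a change of wording with no extra participants or samples. The power of the chosen single-time ANOVA is unaffected: for a 1-SD difference with 21 per group it is 92% if one group differs from the other three, or 76% if two groups lie at the extremes and two midway. The downside is that results on the other outcome and times are no longer confirmatory.

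If the sponsor wants both outcomes confirmatory, one pre-stated test per outcome with Holm's procedure would do it, but at a price. The protocol's formula at 0.025 gives 2(2.241 + 1.282)² = 24.8, so 25 analysed per group and 25 / 0.85 = 29.4, about 30 enrolled. Keeping 21 lowers the formula's power from 90% to Φ(√10.5 − 2.241) = 84%.
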